**4. OBJECTIVES\***

The overall goal of this study is to detect preclinical signs of HAPE by lung ultrasonography and evaluate the effectiveness of acetazolamide at decreasing pulmonary edema by using ultrasound.

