**10. STUDY ENDPOINTS\***

Primary outcome measures: 1.) Pulmonary edema detected in lung ultrasound exams before and after taking acetazolamide.

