### 11. PROCEDURES INVOLVED\*

After informed consent has been obtained, subjects will be randomized to receive either of the study medications medication: 250mg of acetazolamide or a placebo pill. Investigator will be blinded as to which arm of the study the patient is enrolled. Medications will be obtained from the UMass Pharmacy in individual blister packs. We will ensure that acetazolamide and the chosen placebo pill look similar. Any identifying information on the blister pack will be obscured by a black marking pen, if necessary. Medications will then be inserted into small opaque envelopes and marked with only a number. Numbers will be assigned to medications by use of the random number generator function (=RANDBETWEEN(1,30\*)) (\*The final number will depend on the total number of subjects) in Excel with the top half of the list being assigned Acetazolamide and the bottom half placebo pill. The list will then be sorted in numerical order in Excel. When a subject enrolls, a number will be assigned in order. Blinding of the numbers and assigned medications as well as the assembly of the envelopes will be done prior to leaving UMass by PI's faculty advisor who will not be involved in medication administration.

At each of the time points noted in #9, lung ultrasound exams will be done at bedside in a private location to measure the total ultrasound lung comets (an ultrasound finding for pulmonary edema) for a "comet score." One (1) single dose of 250mg acetazolamide or placebo will be given at Everest Base Camp (Data Collection #4) and a comet score will be measured again 12 hours after acetazolamide or placebo is given. Previous studies have shown that comet scores increase with altitude and given that Everest Base Camp is the highest altitude the subjects will be residing at, it is believed that we will find the biggest decrease in comet score if acetazolamide is given at this point. The subject's heart rate and oxygen saturation will also be collected via a pulse oximeter.

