#### **13. Data Analysis and Management\***

Previous studies in lung ultrasonography suggest that a minimum of 14 subjects will be needed to provide 80% power to detect a statistically significant difference in ultrasound lung comets. Between 20-30 total subjects are expected.

For data analysis, Fisher's exact test will be used to compare categorical variables. Continuous variables will be analyzed with paired Student's t-test. Linear regression models will be used to assess correlations between ultrasound lung comets and vital signs. In all cases p values < 0.05 will be considered significant. Data will be reported as mean +/- SD

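### Section 13 plans no estimate or confidence interval for the acetazolamide-minus-placebo difference, so the planned output does not measure the randomised drug effect or its precision

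*Combined protocol and SAP*

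**What the plan says.** Section 4 gives as an aim to "evaluate the effectiveness of acetazolamide at decreasing pulmonary edema by using ultrasound". Section 11 randomises subjects to a single dose of acetazolamide or placebo, intended 1:1, "with the top half of the list being assigned Acetazolamide and the bottom half placebo pill". The dose is given at Data Collection 4 and the comet score is measured again 12 hours later. Section 10 words the primary outcome as a before-and-after measure: "Pulmonary edema detected in lung ultrasound exams before and after taking acetazolamide". It names no between-arm effect measure.

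Section 13 is the whole statistical plan. It assigns Fisher's exact test to categorical variables, a paired Student's t-test to continuous variables, and linear regression to the relation between comets and vital signs. The decision rule is "In all cases p values < 0.05 will be considered significant" and the reporting format is "Data will be reported as mean +/- SD". On size, it states that "a minimum of 14 subjects will be needed to provide 80% power to detect a statistically significant difference in ultrasound lung comets", and adds: "Between 20-30 total subjects are expected". No confidence interval, between-arm estimate or other measure of precision appears in the text supplied. The attached grant proposal, which was not supplied, is cited for background and scanning methods, not for statistics.

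**The concern.** Whether a drug lowers the comet score, and by how much, is a question of estimation. In a placebo-controlled trial the answer is the difference between arms in the change over the 12 hours after dosing, with a statement of its uncertainty. A paired test compares each subject with himself or herself. It does not compare drug with placebo, and a change over 12 hours at Everest Base Camp may occur in either arm without the drug. An SD describes how much subjects differ; it is not a measure of the precision of a treatment effect.

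With a group this small the interval will be wide. If the outcome is a p-value above 0.05, the specified output gives a reader no direct means of separating little or no effect from a large effect estimated imprecisely. A significant result is affected too, since its size and imprecision would also go unstated.

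**Working it through.** **Inputs.** From section 13: threshold 0.05, 80% power with at least 14 subjects, 20 to 30 subjects expected. From section 11: two equal arms, hence 10 to 15 per arm. Assumed, because not stated: two-sided tests, complete pairs, and the same SD of the change score in both arms. Effects are in units of that SD, because no SD of comets is given.

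**The plan's own figure.** The 14 subjects cannot be reproduced, because neither an effect size nor an SD is stated. Solving backwards (noncentral t, two-sided 0.05, 80% power) gives the effect it would imply under each reading:

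| Reading of 14 | Implied effect (SD of change) |
|---|---|
| 14 pairs, paired test | 0.81 |
| 7 per arm, two-sample test | 1.63 |
| 14 per arm, two-sample test | 1.10 |

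**Precision of the between-arm difference in mean change.** Half-width = t(0.975, 2n-2) × √(2/n).

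- n = 10 per arm: 2.101 × 0.447 = 0.94 SD.
- n = 15 per arm: 2.048 × 0.365 = 0.75 SD.

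**Illustration.** Suppose the observed difference is 0.5 SD in favour of the drug, written as -0.5.

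- n = 10: t = 0.5/0.447 = 1.12, p = 0.28, interval -0.5 ± 0.94 = -1.44 to +0.44 SD.
- n = 15: t = 0.5/0.365 = 1.37, p = 0.18, interval -0.5 ± 0.75 = -1.25 to +0.25 SD.

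Both are non-significant, and both intervals include a benefit of more than one SD.

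**Chance of a significant result.** This depends wholly on the unstated true effect. Power of a two-sample comparison of change:

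| True effect (SD of change) | 10 per arm | 15 per arm |
|---|---|---|
| 0.5 | 19% | 26% |
| 0.8 | 40% | 56% |
| 1.10 | 64% | 83% |
| 1.63 | 93% | 99% |

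Non-significance is the more probable outcome only if the true effect is below about 0.93 SD at 20 subjects or 0.74 SD at 30.

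These figures are for a between-arm comparison, which the plan does not name. For the paired test that it does name, applied within one arm, power at 10 and 15 pairs is 29% and 44% for a mean change of 0.5 SD, and 62% and 82% for 0.8 SD. Those figures concern change over time within an arm, not the drug effect.

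**Can the interval be recovered from mean ± SD?** If mean change, SD of change and n are given per arm, yes. If only means and SDs by time point are given, it needs the pre/post correlation r. With equal SDs at the two times, SD of change = raw SD × √(2(1-r)). For r from 0 to 0.9 the half-width runs from 1.33 to 0.42 raw SD at 20 subjects, and from 1.06 to 0.33 at 30. The plan does not say which quantities will be reported.

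**The case against.** The strongest reply is that this is a short study plan for an ethics board. It omits intervals but does not forbid them, and they can be computed later from the same data. Mean ± SD may well cover the change score, which is what a paired t-test analyses. Even if only time-point means are reported, their difference in complete pairs is the mean within-subject change, and an exact paired p-value with n then gives back the SD of the change when the mean change is not zero. All of this stands, so it would be wrong to say that the size of the effect could never be recovered. What remains is that the plan commits to none of these outputs.

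A reader might go further in two ways that the documents do not support:

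- **That a non-significant result is the likely one.** The plan gives no effect size or SD, and two-sample power at 20 to 30 subjects runs from 19–26% at 0.5 SD to 93–99% at 1.63 SD, the effect implied by one reading of the plan's own 14 subjects.
- **That the plan would read p ≥ 0.05 as proof of no effect.** Section 13 says only what counts as significant. It has no rule for interpreting a result that is not.

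It is also fair to say that the more basic gap is the missing between-arm contrast, and that an interval follows once that contrast is named. The two belong in one change.

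**Conclusion.** The concern holds in a limited form. As written, section 13 yields no estimate of the acetazolamide-minus-placebo difference and no statement of its precision, so the planned output does not answer the effectiveness objective in section 4. The interval that is missing would be about ±0.94 SD of the change at 20 subjects and ±0.75 SD at 30, assuming equal arms, complete pairs, a common SD and two-sided 95% coverage. Withdrawals, which section 15 allows for, would widen it. A non-significant result could thus be compatible with a large benefit. Its probability cannot be stated from the documents. The data remain usable and nothing in the conduct of the trial has to change, so this is a change that should be made to the analysis text rather than a flaw that invalidates the study.

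**What to change.** In section 13:

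1. Make the primary result the acetazolamide-minus-placebo difference in comet-score change from Data Collection 4 to Data Collection 5, with its two-sided 95% confidence interval.
2. Report the mean change, its SD and n for each arm.
3. State that a non-significant result will be interpreted from the interval, not as absence of effect.
4. Keep mean ± SD by time point as description only.

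The primary outcome in section 10 should be reworded to match. The cost is analysis wording, with no added subjects, scans or data. It is more than an editorial change, because a between-arm contrast replaces the paired test as the primary analysis. The small downside is that the imprecision becomes visible and a null result can no longer be presented as absence of effect.

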#### **14. PROVISIONS TO MONITOR THE DATA TO ENSURE THE SAFETY OF SUBJECTS\***

The study is designed to give only one (1) dose of medication. If there is any adverse reaction to acetazolamide, subject will be evaluated by PI or WMS trip leaders, who are trained in emergency medicine and wilderness medicine. A decision will be made to whether or not to continue the study for the subject. Common side effects include:

- headache
- diarrhea
- feeling or being sick, loss of appetite, thirst, or a metallic taste in the mouth
- lightheadedness
- looking flushed
- a need to pass urine more often than normal
- tiredness or irritability
- feeling over-excited
- a tingling or numbness in the fingers or toes, or coldness in the extremities.

Symptomatic treatments will be provided as needed. Subject will be given a choice whether or not to continue with the study, which will only involve ultrasound scanning, for the rest of the trek.

## **H00014860 Acetazolamide on High-Altitude Pulmonary Edema**

**Version 2 – 02/10/2018**

### **INVESTIGATOR STUDY PLAN**

In the case that ultrasound imaging picks up findings that could indicate that subject is at risk of developing high-altitude pulmonary edema, in addition to any subject displaying signs of severe altitude illness, they will be treated and evacuated as determined necessary by the WMS medical providers present. The 2018 WMS trip leaders are Emergency Physicians who are trained in wilderness medicine and have substantial experience diagnosing and treating altitude illness and arranging evacuations in Nepal. Participants requiring evacuation will be accompanied by a guide. In the event that an individual cannot descend on foot, helicopter evacuation is possible up to Everest Base Camp. All WMS trip participants are required to carry evidence of Evacuation and Medicine Travel insurance that covers high altitude. Participation in this research project will not dictate or change treatment or evacuation in any way.

This study involves no more than minimal risk to subjects, and therefore will not utilize a DSMB.

#### **15. WITHDRAWAL OF SUBJECTS WITHOUT THEIR CONSENT\***

Subjects may be withdrawn from the study if they become exceedingly ill or injured, unconscious, or require evacuation. In this case, the data already collected will remain in the study, but subjects will not complete future data points.

#### **16. RISKS TO SUBJECTS\***

This study poses minimal risks to participants, mainly the brief exposure of skin to ultrasound gel and probe during image acquisition. Image acquisition happens while indoor inside lodging and duration should not exceed 5 minutes per session. The study is 3 weeks and participants can withdraw at any time if they feel uncomfortable with continuing the study.

There is also a risk of breach of confidentiality. Though we will not be recording patient names or medical record numbers, we will be tracking subject demographics tied to a unique identifier along with recorded ultrasound images.

Acetazolamide is a drug that has been approved by FDA for use of prevention of acute mountain sickness. Potential side effects including but not limited to lightheadedness, paresthesia's of fingers and toes, change in urination frequency, and change in taste of beverages. These side effects are more common in the persistent use of acetazolamide and are unlikely when taking only one single dose. If subject has an allergic reaction to acetazolamide, subject will be evaluated and treated for allergic treatment, if necessary. Treatment includes but not limited to diphenhydramine, prednisone, and intramuscular epinephrine

While being at high altitude can cause physical discomfort and psychological stress as well as the risk of developing high altitude illness, this is a risk that participants have chosen to undertake prior to being enrolled in the study. Participating in this study does not add to this risk and may even help subjects be more aware of any altitude illness symptoms that are developing.

**H00014860 Acetazolamide on High-Altitude Pulmonary Edema**

**Version 2 – 02/10/2018**

**INVESTIGATOR STUDY PLAN**

**17. POTENTIAL DIRECT BENEFITS TO SUBJECTS\***

N/A

**18. VULNERABLE POPULATIONS\***

N/A

**19. MULTI-SITE RESEARCH\***

This study is being conducted simultaneously with study #H00014129. While the studies are on the same subjects, the studies are expected to minimally impact each other. The main potential effect the studies could have on each other is the time that will take for each to be completed at a time point, however neither data collection is expected to take more than 20 minutes per subject. The pulmonary ultrasound measurements of study #H00014860 are short duration and not expected to impact cognitive function or the ability of subjects to answer questions on the concussion software. The concussion apps in this study do not require physical exertion except minimal effort during a short time standing and balancing and are not expected to impact pulmonary edema or the ultrasound measurements.

Study #H00014860 involves a single dose of acetazolamide or placebo at Everest Base Camp. The concussion app data for this time point will be collected before the medication is given and therefore should not be impacted. An additional data point 12 hours later at Everest Base Camp will be added to assess any effect of the medication on the concussion app data for study #H00014129. While this study's main goal is not to assess the effect of acetazolamide on the cognitive functions measured by the concussion apps, it may add useful information both for this study and for study #H00014860. The half-life of immediate release acetazolamide is 5-6 hours and is expected to have been excreted prior to the next time point six days later after descent.

**20. COMMUNITY-BASED PARTICIPATORY RESEARCH\***

N/A

**21. SHARING OF RESEARCH RESULTS WITH SUBJECTS\***

Since ultrasound images will not be definitely reviewed until after the trek is completed, we will not be sharing the results with the subjects during the trek. However, as we consent each subject, they will be asked whether or not if they want the final results to be shared with them after the study is completed. If the subject chooses to have results to be shared with them, they will be contacted via subject's preferred contact method after all the ultrasound images reviewed and results have been gathered. Research results will not be shared with anyone else.

## **H00014860 Acetazolamide on High-Altitude Pulmonary Edema**

**Version 2 – 02/10/2018**

### **INVESTIGATOR STUDY PLAN**

In the case that ultrasound imaging picks up findings that could potentially indicate that subject is at risk of developing high-altitude pulmonary edema, necessary steps will be taken as described in #14

#### **22. SETTING**

Altitude illness has the highest incidence at extreme altitudes, especially over 14,000 feet, which is limited in the U.S. to a handful of summits, making it difficult to study domestically. However, this altitude and higher is easily found in the Himalayan mountains. Nepal is a well-established site for altitude research.

Data collection will take place in rural Nepal in the Himalayan mountains along the usual approach route to the Mt. Everest basecamp. Image acquisition of the subjects will take place in the dining area of tea houses (local hostels with attached restaurants). The dining rooms are the only areas of the tea house that are heated and lit in the evening hours.

Dining rooms serve as points of congregation for the trip. Though they are public spaces, participant privacy will be accommodated by setting up a research station in a quiet room.

#### **23. RESOURCES AVAILABLE**

Principal Investigator: Design and oversee the project. Obtain funding and necessary approvals. Set up hand-held ultrasound tablets. Travel to Nepal and collect data. Acquire images. Publish results. PI is a residency-trained physician in emergency medicine, currently in completing emergency ultrasound fellowship with extensive experience in bedside ultrasonography. PI also has experience in backpacking and camping in remote environments as well as experience in international travel.

Faculty Advisor: Will accompany PI during the trek and oversee another research project. The faculty advisor has experience with conducting research in rural Nepal at the proposed site for multiple prior studies. The faculty advisor is fellowship-trained in wilderness medicine and has significant experience in backpacking and camping in remote environments, international travel including Nepal and Asia, required travel medications/vaccinations, and mountain trekking safety. The faculty advisor has knowledge of the culture, customs, and society in Nepal as well as some basic knowledge of the Nepali language. The faculty advisor also has significant experience ascending to high altitude, identifying and treating high altitude illnesses, and potential evacuation options should an emergency arise.

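### The faculty advisor who packs the coded envelopes also joins the trek, so someone in the field could work out each subject's arm

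*Combined protocol and SAP*

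**What the plan says.** Section 11 states that the investigator is blinded. It builds the allocation from an Excel list, "with the top half of the list being assigned Acetazolamide and the bottom half placebo pill", sorted by number. Subjects then receive numbers sequentially: "When a subject enrolls, a number will be assigned in order". The task described as "Blinding of the numbers and assigned medications as well as the assembly of the envelopes" is given to the PI's "faculty advisor who will not be involved in medication administration" and is completed before the team leaves UMass. The drug itself comes from the hospital side: "Medications will be obtained from the UMass Pharmacy in individual blister packs".

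Section 23, describing the faculty advisor's role, says: "Will accompany PI during the trek and oversee another research project". Section 19 describes study #H00014129, run at the same time on the same subjects, and says: "An additional data point 12 hours later at Everest Base Camp will be added to assess any effect of the medication".

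No section says that the advisor is blinded, where the list is kept during the trek, who holds the code, or that the advisor is kept away from post-dose assessments or image reading.

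**The concern.** Section 11 separates the person who prepares the coded envelopes from the person who gives the pill. That protects the moment of dosing but nothing after it. Blinding also has to hold for whoever assesses subjects after the dose, whoever is in daily contact with the person scanning, and whoever reads the images. Section 23 places the preparer in the same small travelling group as the blinded PI.

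What is at stake is the credibility of a blinded comparison in a small trial. If someone in the group can derive the arms, that knowledge could reach the person scanning. It could also colour a post-dose assessment that the same person oversees. Afterwards, nobody could show from the protocol that this did not happen.

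**Working it through.** The plan gives no figure on this point and no arithmetic tests it. The check is a cross-reading of roles and access.

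1. **Who can know which number is which drug.** Section 11 gives the advisor the blinding of numbers and the packing. It describes making the list in the passive voice, so who generates it is not explicit. This does not matter, because a person who puts active drug or placebo into a numbered envelope must know at that moment which number gets which.

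2. **What is needed to go from number to subject.** Numbers follow enrolment order, so the k-th subject enrolled receives the k-th number. List plus enrolment order therefore gives every subject's arm. The list comes from the advisor's task. The order is created in Kathmandu, where section 30 has the PI obtain consent.

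3. **Whether both pieces can meet in the field.** Section 23 puts the advisor on the trek with the PI. No section keeps the list at UMass or keeps the enrolment log from the advisor.

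4. **When it matters.** By the section 9 itinerary, numbers can be assigned from 26 March, dosing and the repeat scan (Data Collection 4 and 5) are on 7 April, and the last scan is on 13 April. Assignment to dosing is 5 + 7 = 12 days, during which the two pieces could be put together. The treatment comparison itself depends mainly on the scan at dosing and the one 12 hours later, so that short interval is where knowledge of the arm could do most harm.

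5. **Which data are exposed.**
   - *Companion 12-hour point (section 19).* Direct, if the project in section 23 is #H00014129. Section 23 does not name it, but #H00014129 is the only concurrent study described and it uses the same subjects.
   - *Comet score (sections 10 and 11).* Indirect. Section 23 has the PI acquire the images, section 21 defers definitive review until after the trek, and section 26 has an expert reviewer interpret them. Bias would need disclosure to the PI or a reader who knows the arms. Section 26 does not identify the reader or state that the reader is blinded, and it gives study personnel access to images without excluding the advisor.

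6. **What the stated safeguard covers.** It covers giving the medication. It does not cover contact with subjects and the PI, post-dose assessment, or image reading.

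**The case against.** The strongest reply is that opportunity is not knowledge. The advisor's task ends before any subject has a number. Nothing says that the advisor carries the list, remembers up to 30 randomly ordered entries, or sees the enrolment log. A reader might infer that all allocations are known to a member of the group from enrolment to the last scan; the documents do not support that. They show only that the arms could be worked out.

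A reader might also infer that the advisor could influence who continues or is evacuated, since section 23 cites experience with altitude illness and evacuation. The documents do not support that either. Section 14 gives evaluation of adverse reactions to the PI or the trip leaders, and treatment and evacuation to the trip's medical providers. It adds that taking part in the research will not alter those decisions. The advisor is not named as a trip leader.

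Two further replies have weight. The primary endpoint is partly insulated by a blinded PI and later reading. The most exposed data belong to another protocol, whose assessors and blinding cannot be seen here, and concussion-app results are not endpoints in section 10. Selection is not at issue: all eligible participants are to be recruited (section 24) and numbers are given in order.

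These replies limit the point but do not remove it. The protocol relies on one named safeguard, and that safeguard does not reach the period after dosing. Section 19 itself says the 12-hour companion data may be useful to this study.

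**Conclusion.** The point holds as a weakness in a stated arrangement, and it is more than missing detail: the person given the allocation task is also given a field role, and only dosing is fenced off. Up to 20 to 30 allocations could be derived by someone on the trek. The effect on results cannot be quantified from the documents, and nothing suggests that bias is certain or large.

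The conclusion rests on two inferences: that packing reveals the number-to-drug link, which is close to unavoidable, and that the project in section 23 is #H00014129, which is likely but not stated. If the second is wrong, the direct exposure of the 12-hour companion data falls away, but the advisor's presence alongside the PI remains. This is best treated as a cheap improvement to make before departure.

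**What to change.** In section 11, transfer list generation, packing of the numbered envelopes and custody of the code to the UMass Pharmacy, which already supplies the drug, or to another person who does not travel and has no assessment role. State that the code stays sealed at UMass until all comet scores are locked, and name its holder.

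If the advisor must keep the task, state in section 11 that the list is left sealed at UMass, and in sections 19 and 23 that the advisor takes no part in post-dose assessment or image reading in either study. This is weaker, because the advisor will still have seen the list, but it closes most of the gap.

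The cost is a small preparation task and a few sentences of protocol text, with no added field staff. The pharmacy or other person must agree to do it; the documents describe the pharmacy only as the source of the drug. The fallback also takes the advisor out of the 12-hour companion assessment, so someone else would have to do it.
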